8.2. Setting

The primary analysis of this study will include all people at least 12 years of age with at least one vaccine claim (primary analysis: BNT162b2; sensitivity analyses: any Mrna, any authorized vaccine) between 11 December 2020 and 08 July 2021 (or latest date available) from the HealthVerity HealthCare Database. Patients included in the study will be required to have 12 months of continuous medical enrollment prior to the receipt of their first vaccine and have no evidence of a SARS-CoV-2 infection in the year prior to being vaccinated.

The study population will be stratified into two cohorts: non-immunocompromised and immunocompromised. Patients with IC conditions will be identified using a modified implementation of an algorithm developed by Greenberg et al – and later modified and

expanded by Patel et al – for administrative claims based on claims and healthcare records identified in the 12 month baseline period.^{24, 25}

8.2.1. Inclusion criteria

Patients must meet all of the following inclusion criteria to be eligible for inclusion in the study:

1. Unique enrollees in the HealthVerity Vaccine dataset any time **after** 10 December 2020
2. At least 12 years on the index date (ie, first vaccination date)
3. No evidence of prior COVID-19 infection (a medical claim, pharmacy claim, or chargemaster record with an International Classification of Diseases, 10th Revision, Clinical Modification (ICD-10-CM) diagnosis code of U07.1) in the 12 months prior to the index date
4. Have 12 months of continuous enrollment with medical benefits (with or without pharmacy benefits) prior to the index date

Subjects with an IC condition were identified via an algorithm originally developed and validated by Greenberg et al²⁴ for use in administrative claims database studies. For this study, this algorithm will be modified and expanded based on expert medical opinion. The algorithm is depicted in [Figure 1](#).

Subjects will be identified as immunocompromised if they had ≥ 1 hospitalization or ≥ 2 outpatient visits on separate dates with an ICD-10-CM code on a healthcare claim indicating an IC condition or if they had usage of specific immunosuppressive medications during the 12-month baseline period. The IC case definition will incorporate 8 groups based on clinical diagnoses only, 1 group based on both clinical diagnoses and usage of immunosuppressive medication, and 2 other groups based on usage of immunosuppressive medication only, for a total of 11 groups with an IC condition ([Figure 1](#)). Subjects with >1 IC condition will also be assessed, for a total of 12 mutually exclusive groups for inclusion in this study. The list of ICD-10-CM codes used to identify IC cases by diagnosis and list of immunosuppressive medications are shown in the Annex.

Eight of the disease groups will include subjects with 1) symptomatic human immunodeficiency virus (HIV)/acquired immunodeficiency syndrome (AIDS); 2) solid malignancy; 3) bone marrow transplant; 4) organ transplant (excluding bone marrow); 5) rheumatologic or other inflammatory condition; 6) a primary immunodeficiency; 7) other immune conditions; and 8) chronic kidney disease (CKD) or end stage renal disease (ESRD). Subjects in these IC groups (shown as “Group 1” in [Figure 1](#)) will be further stratified by treatment status: those with usage of immunosuppressive medications for >14 days anytime during the baseline period and those without any evidence of >14 days of usage of an immunosuppressive medication during the baseline period. Subjects with a bone marrow or

organ transplant will be further stratified by those who received their 1st vaccine dose >100 days prior to their transplant and those who received it <100 days prior to their transplant. Subjects with a solid malignancy will be further stratified by their treatment type: chemotherapy or radiation therapy or immunomodulator, or a mix of these treatments.

The 9th subject group (shown as “Group 2” in [Figure 1](#)) will include those with a hematologic malignancy, required to have usage of an immunosuppressive medication (chemotherapeutic agent, immunomodulator, or systemic corticosteroid) for >14 days anytime during the baseline period; this subject group will be further stratified by their use of an immunosuppressive medication >6 months or ≤ 6 months prior to their index date.

The 10th subject group will include subjects with usage of an immunosuppressive medication (chemotherapeutic agent, immunomodulator, or systemic corticosteroid excluding low-dose [<60mg/day] prednisone) for >14 days anytime during the baseline period, but without any ICD-10-CM diagnosis codes indicating the above listed IC conditions on a healthcare claim anytime during the baseline period. Subjects with >14 days usage of antimetabolites anytime during the baseline period will be excluded from this subject group and placed in the 11th subject group.

[figure not shown]
This algorithm differs from that used in Greenberg et al²⁶ by the following modifications, considered relevant for COVID-19 based on expert medical opinion: the inclusion of subjects with a solid malignancy who had radiation therapy or any treatment mix; the separation of subjects with a bone marrow transplant and those with an organ transplant; the inclusion of chronic inflammatory demyelinating polyneuropathy and immune thrombocytopenic purpura in the “rheumatologic or other inflammatory condition” group; the inclusion of sickle cell disease, asplenia, and psoriatic arthritis in the “other immune disorders” group; the addition of subjects with primary immunodeficiencies and those with CKD or ESRD; the requirement that subjects with a hematologic malignancy have evidence of usage of an immunosuppressive medication; the reclassification of subjects with only usage of an immunosuppressive medication; the removal of subjects with usage of only low dose prednisone; and the inclusion of an ad-hoc group of subjects who had taken anti-metabolites. Additionally, the following subcategories will be created: the first 9 subject groups were stratified according to treatment status; organ transplant subjects will be stratified according to time of receipt of the first COVID-19 vaccine dose in relation to the date of transplant; and subjects with hematologic malignancy will be stratified by time of receipt of treatment relative to their 1st vaccine dose.

When categorizing subjects with the different types of IC conditions, all the subject groups will be mutually exclusive. Subjects meeting the criteria for classification into only a single IC group will be classified accordingly into subject groups 1-11. Any subjects meeting the criteria for classification into multiple IC groups will be categorized into the >1 IC condition group (12th subject group).

All subjects will be grouped into an overall study population consisting of subjects identified as having an IC condition or not (i.e., non-IC). Subjects with an IC condition will be further categorized into the specific IC condition groups.

Figure 1: Algorithm to define immunocompromising conditions

Algorithm for case definitions of IC conditions in HealthVerity US claims database

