8.3. Variables

Table 1. Immunocompromising Conditions definition

Variable	Role	Data source(s)	Operational definition
Immunocompromising Conditions	Cohort Definition	HealthVerity Vaccine Data	
Subjects will be categorized into the following 12 mutually exclusive IC groups based on the algorithm detailed in Figure 1:
 
Symptomatic HIV/AIDS, solid malignancy, bone marrow transplant recipients, organ transplant recipients, rheumatologic or other inflammatory conditions, primary immunodeficiencies, other intrinsic immune conditions, chronic kidney disease or end stage renal disease, hematologic malignancy, immunosuppressive treatment only, antimetabolites only, or >1 IC condition.

PFIZER CONFIDENTIAL

Table 1. Immunocompromising Conditions definition

Variable	Role	Data source(s)	Operational definition
			
Subjects falling into more than one of these categories will be categorized as having >1 IC condition.
 
At a minimum, subjects will be required to have one inpatient claim or two outpatient claims on separate days with the IC condition of interest in the baseline period. In cases when >14 days of treatment are required it will be based on the dispensed day supply or distinct days of treatment in the baseline period.
 
The main diagnosis codes to identify IC conditions are presented in ANNEX 1. LIST OF STAND ALONE DOCUMENTS.

Table 2. Vaccination Status definitions

Variable	Role	Data source(s)	Operational definition
Any vaccination	Cohort Definition	HealthVerity Vaccine Data	
Patients with a claim for any vaccine will be considered vaccinated with any vaccine based on the following codes:
 
Pfizer/BioNTech: 91300, 0001A, 0002A, 59267100001, 59267100002, 59267100003
 
Moderna: 91301, 0011A, 0012A, 80777027310, 80777027399, 80777027315, 80777027398
 
Johnson & Johnson: 91303, 0031A, 59676058005, 59676058015
 
Source: https://www.cdc.gov/vaccines/programs/iis/COVID-19-related-codes.html

Fully Vaccinated	Cohort Definition	HealthVerity Vaccine Data	
Patients will be considered fully vaccinated if they meet any of the following definitions:
 
Two claims for Pfizer/BioNTech vaccine on separate days with >14 days of follow-up after the 2nd vaccination date. No claims for any other vaccines are allowed.

PFIZER CONFIDENTIAL

Table 2. Vaccination Status definitions

Variable	Role	Data source(s)	Operational definition

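### Pharmacy benefits are optional, yet groups 9-11 and the treated/untreated split of groups 1-8 treat absence of drug evidence as no drug use

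*Combined protocol and SAP*

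**What the plan says.** Criterion 4 in section 8.2.1 requires 12 months of "continuous enrollment with medical benefits (with or without pharmacy benefits) prior to the index date". Section 8.2 likewise asks only for continuous medical enrollment.

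Drug evidence decides classification in several places:

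- Section 8.2.1 describes the groups that are not purely diagnostic as "1 group based on both clinical diagnoses and usage of immunosuppressive medication, and 2 other groups based on usage of immunosuppressive medication only". That is three of the 11 groups.
- Hematologic malignancy (group 9) is "required to have usage of an immunosuppressive medication (chemotherapeutic agent, immunomodulator, or systemic corticosteroid) for >14 days anytime during the baseline period". The footnote to Annex 3 repeats this.
- Groups 1-8 are divided by treatment status. The untreated side consists of "those without any evidence of >14 days of usage of an immunosuppressive medication during the baseline period".
- Table 1 in section 8.3 says of the 14-day requirement that "it will be based on the dispensed day supply or distinct days of treatment in the baseline period".

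Section 8.2.1 then places every subject in either the IC or the non-IC population. It has no category for subjects whose drug exposure cannot be determined. Section 8.7 plans incidence rates, a risk difference between the two cohorts, and results by IC condition.

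**The concern.** The eligibility rule and the classification rule do not fit together. A subject without pharmacy coverage can have more than 14 days of a dispensed immunosuppressant with no record of it in the data. The plan reads that silence as no use, with three results:

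- In groups 1-8, a treated subject is counted as untreated.
- A subject who belongs in groups 9-11 is counted as non-IC, unless another IC group applies.
- A subject who belongs in the group with more than one IC condition can fall back to a single-condition group.

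Results in specific IC conditions are a secondary objective in section 7, and the treatment strata are built into the algorithm. At stake are the size and make-up of groups 9-11 and the incidence rate in every stratum labelled untreated.

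A related but separate issue concerns hematologic malignancy. A subject with those codes and no qualifying drug is non-IC by definition (unless another group applies), even when pharmacy data are complete. Missing pharmacy data then add treated patients to the same comparator.

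**Working it through.** The plan states no sample size, event count or share without pharmacy benefits, so it has no figure to reproduce. The inputs below are assumptions, chosen to show a range.

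**Inputs**
- *u*, share of subjects without visible pharmacy data: 10-30%.
- *a*, share of those subjects' drug use still seen in medical claims: 0, then 50%.
- *m* = *u*(1 − *a*), share of true drug users who are missed.
- *t*, share of a diagnosis group truly treated: 30-50%.
- True treated/untreated rate ratio: 2.0.

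**Step 1: the 'untreated' stratum in groups 1-8.** The share truly treated is *c* = *tm*/(1 − *t* + *tm*). The observed ratio is 2/(1 + *c*). With *a* = 0, so that *m* = *u*:

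| *t* | *m* | *c* | Observed ratio |
|---|---|---|---|
| 0.3 | 0.1 | 0.03/0.73 = 4.1% | 1.92 |
| 0.3 | 0.3 | 0.09/0.79 = 11.4% | 1.80 |
| 0.5 | 0.1 | 0.05/0.55 = 9.1% | 1.83 |
| 0.5 | 0.3 | 0.15/0.65 = 23.1% | 1.62 (1.625) |

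The incidence rate in the untreated stratum is inflated by the factor 1 + *c*, that is, by 4-23%.

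**Step 2: allowing for medically billed drugs.** Setting *a* = 0 is the worst case for that input. With *a* = 50%, *m* is 5-15%. Then *c* runs from 0.015/0.715 = 2.1% to 0.075/0.575 = 13.0%, and the ratio reads 1.96 to 1.77.

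**Step 3: groups 9-11.** Capture of their true members is 1 − *m*: 90-70% with *a* = 0, and 95-85% with *a* = 50%.

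**Step 4: pooled IC versus non-IC.** Let *p* be the true IC prevalence (10-20%) and *g* the share of IC subjects who qualify only through groups 9-11 (5-30%). Take true rates of 2 in IC and 1 in non-IC. The share of the non-IC cohort that is truly IC is *pgm*/(1 − *p* + *pgm*).
- Worst case (*p* = 0.2, *g* = 0.3, *m* = 0.3): 0.018/0.818 = 2.2%, so a true difference of 1.00 reads as 0.98.
- Mild case (*p* = 0.1, *g* = 0.05, *m* = 0.1): 0.0005/0.9005 = 0.06%, so it reads as 1.00 after rounding.

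The error matters in the drug-defined groups and strata, and is small in the pooled contrast. Step 4 covers only missing pharmacy data. It does not include the hematologic malignancy subjects who are non-IC by definition.

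**The case against.** Several points on the other side stand.

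- **Medical claims.** Table 1 also counts distinct days of treatment, so drugs administered and billed medically remain visible. The loss concerns mainly pharmacy-dispensed drugs.
- **Benefit status is not data visibility.** Section 8.4 describes linked pharmacy services and integrated electronic records. Some subjects without a recorded pharmacy benefit may still have drug records. The plan neither says so nor requires a check.
- **Not every stratum is affected.** Solid malignancy is split by "chemotherapy or radiation therapy or immunomodulator, or a mix of these treatments". Radiation is not a drug claim, and the transplant-timing split rests on dates.
- **The ratio is illustrative.** Section 8.7 names no treated/untreated ratio as an analysis. The strata are defined, but the contrast is used here only to show scale.
- **Hematologic malignancy.** The drug requirement is a disclosed modification of the algorithm, so that part is a matter of definition, separate from criterion 4.
- **General safeguards.** Section 8.7 allows sensitivity analyses that vary continuous enrollment and the IC case definition. Sections 8.8 and 8.9 acknowledge incomplete variables and misclassification. None of these names pharmacy coverage or links it to the drug-defined groups, so the gap remains.

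A reader might infer that the misclassification is differential and materially biases the primary IC versus non-IC contrast toward no difference. The documents do not support that. Nothing in them links pharmacy coverage to the breakthrough outcome, eight of the 11 groups need diagnosis codes only, and step 4 shows a shift of at most about 0.02 on a difference of 1.00.

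**Conclusion.** The concern holds for groups 9-11, for the treated/untreated split of groups 1-8, and for movement out of the multiple-condition group. Followed as written, the plan will misclassify users of dispensed drugs whose dispensing is not captured. How many there are cannot be determined from the documents.

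Under the assumed inputs, with no use visible in medical claims, 4-23% of the untreated stratum is really treated and a true ratio of 2.0 reads as 1.92 to 1.62. With half of the use visible, the figures are 2-13% and 1.96 to 1.77. The effect of missing pharmacy data on the pooled contrast is likely small. The placement of hematologic malignancy subjects without a qualifying drug in the non-IC comparator is a separate matter that complete pharmacy data would not cure.

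**What to change.** 1. Keep criterion 4 for the full cohort. Keep anyone with observed qualifying drug use, from a pharmacy or a medical claim, in groups 9-11 or the treated strata. Requiring pharmacy enrollment to enter those groups would remove subjects who are correctly identified from medical claims.
2. In groups 1-8, assign 'untreated' only to subjects with 12 months of baseline pharmacy enrollment or verified pharmacy capture. Label the others 'treatment status unknown'.
3. Prespecify a named sensitivity analysis of groups 9-11, the treatment strata and the IC versus non-IC contrast. Restrict both cohorts, including the non-IC comparator, to subjects with pharmacy benefits. This deals with possible drug-only subjects who remain in the full non-IC cohort.
4. Show subjects with hematologic malignancy codes but no observed qualifying drug as a separate row outside the non-IC comparator. The definition of group 9 need not change.
5. Report the share without pharmacy benefits by cohort.

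The cost is some analysis-plan wording, a coverage flag, one restricted analysis and one extra row. There will be fewer subjects in the untreated strata and in the restricted analysis. How many fewer cannot be computed without the share in item 5.

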ANNEX 3. ICD-10 CODE LIST

IC Condition	ICD-10 Code
HIV/AIDS*	B20-B24
Solid malignancy	
Organ/system malignant tumors	C00-C07; C11-C19; C22-C80; Z85
Neuroendocrine tumors	C7A; C7B; D3A
Neoplasms of uncertain behavior	D00-D49
Bone marrow transplant	Z94.81
Organ transplant	
Complications of transplanted organ	T86
Organ transplant status	Z94 except Z94.81; Z98.85
Rheumatologic or other inflammatory condition	
Sarcoidosis	D86
Amyloidosis Not Otherwise Specified (NOS)	E85
Familial Mediterranean fever	E85.0; M04
Amyloidosis Not Elsewhere Classified (NEC)	E85.1; E85.3; E85.8
Multiple sclerosis	G35
Other Central Nervous System (CNS) demyelination	G36; G37.1; G37.3; G37.8; G37.9
Acute infective polyneuritis	G61.0; G61.9
Acute myocarditis	I40
Polyarteritis nodosa and other	M30
Allergic alveolitis/pneumonitis NOS	T78.40; J67.9
Other alveolar pneumonopathy	J84.01; J84.02; J84.09

PFIZER CONFIDENTIAL

IC Condition	ICD-10 Code
Enteritis and colitis	K50-K52
Lupus erythematosus	L93.0; L93.2; M32
Diffuse connective tissue disease	L94; M35.8; M35.9
Arthropathy with infection	M12.9; M01.X0; M02.10
Crystal arthropathies	M11
Rheumatoid arthritis/inflammatory polyarthropathy	M05-M14
Inflammatory spondylopathies	M46
Polymyalgia rheumatica	M31.5; M35.3
Chronic inflammatory demyelinating polyneuropathy	G61.81
Immune thrombocytopenic purpura	D69.3
Primary Immunodeficiency	
X-linked agammaglobulinemia	D80.8
Common variable immunodeficiency	D83.1; D83.2; D83.8; D83.9
Immunoglobulin A (IgA) deficiency	D80.2
Immunoglobulin G (IgG) sub-class deficiency	D80.3
Severe combined immunodeficiency	D81.1
Di George syndrome	D82.1
Wiskott-Aldrich	D82.0
Ataxia telangiectasia	G11.3
Interferon-gamma/Interleukin 12 axis deficiencies	D84.89
Persistent complement, properdin or Factor B deficiency	D84.1
Received eculizumab for >14 days in the baseline period	
Chronic granulomatous disease	D71
Chediak-Higashi	E70.330
Leukocyte adhesion deficiency	D72: Genetic anomalies of leukocytes
Myeloperoxidase deficiency	D72.89: Other specific disorders of White Blood Cells (WBCs)

PFIZER CONFIDENTIAL

IC Condition	ICD-10 Code
Other immune conditions	
Disorders of immune mechanism	D89
Neutropenia	D70
Functional disorders of neutrophils	D71
Genetic anomalies of leukocytes	D72.0
Decreased leukocyte count	D72.81
Leukocyte disease NEC	D72.89
Leukocyte disease NOS	D72.9
Myelofibrosis	D75.81
Blood diseases NEC	D47.4; D75.89; D75.9; D89.2
Blood diseases NOS	D75.9; D75.89
Immunologic findings NEC	R76; R83.4-R87.4; R89.4

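### Annex 3 does not implement the primary immunodeficiency group as sections 8.2.1 and 8.3 define it: a drug line sits in a diagnosis-only group, and D83.0 and most D80 codes fall in no IC group

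*Combined protocol and SAP*

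**What the plan says.** Section 8.2.1 describes "8 groups based on clinical diagnoses only", one group needing both a diagnosis and drug use, and two resting on drug use alone, "for a total of 11 groups with an IC condition". Adding the class for more than one condition gives the count "for a total of 12 mutually exclusive groups for inclusion in this study". The numbered list of the eight includes "6) a primary immunodeficiency; 7) other immune conditions". Table 1 in section 8.3 sets the minimum evidence for a condition at one inpatient claim, or two outpatient claims on different days.

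Annex 3 supplies the codes. Under Primary Immunodeficiency it lists, among others, D80.8, D80.2 and D80.3, and gives common variable immunodeficiency as "D83.1; D83.2; D83.8; D83.9". Directly below the complement-deficiency row (D84.1) stands "Received eculizumab for >14 days in the baseline period", with no code.

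Section 8.2.1 treats anyone not identified as IC as non-IC. Section 8.7 plans breakthrough incidence for each IC condition, and vaccine effectiveness (VE) for the IC groups as an exploratory aim.

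**The concern.** The code list is what the programmer will run, and here it differs from the text it is meant to carry out. The group is declared diagnosis-only, yet it contains a drug criterion whose operation is not stated. The listed codes also have gaps that the annex does not explain.

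This group is an addition to the source algorithm (section 8.2.1), so the sensitivity and specificity quoted in section 8.9 do not cover it. The code list is its only definition. Section 6 says the study should help show which IC conditions go with reduced VE. An estimate for a group whose membership depends on an unstated rule and an incomplete list is hard to read for that purpose.

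**Working it through.** **1. Group count.** From section 8.2.1: 8 + 1 + 2 = 11, and 11 + 1 = 12. Both stated totals are reproduced.

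**2. The eculizumab line against the text.**

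- *As a separate route into the group:* primary immunodeficiency becomes diagnosis-or-drug. The structure is then 7 diagnosis-only + 1 diagnosis-or-drug + 1 diagnosis-and-drug + 2 drug-only = 11. The total is unchanged, but eight diagnosis-only groups become seven. The Table 1 claim minimum is also bypassed for these subjects.
- *As a qualifier of the D84.1 row:* that row needs a diagnosis and more than 14 days of drug use. The group is again not diagnosis-only, and D84.1 subjects without the drug drop out of it.

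The two readings select different people. Under the first, assignment is also unclear. The group 10 rule in section 8.2.1 excludes only subjects with a listed diagnosis code. If eculizumab counts as an immunosuppressive medication, a user with no listed diagnosis meets groups 6 and 10 and moves to the class for more than one condition. Section 8.7 instead excludes from group 10 anyone already in one of the nine condition groups, which leaves that user in group 6. The medication list is not in the annexes available to me, so whether eculizumab is on it cannot be checked.

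**3. Code match.** Each fourth-character position in D80, and D83.0 with its listed neighbours, was compared with every group in Annex 3.

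| Category | Listed (all under primary immunodeficiency) | In no IC group |
|---|---|---|
| D80 | D80.2, D80.3, D80.8 | D80.0, D80.1, D80.4-D80.7, D80.9 |
| D83 | D83.1, D83.2, D83.8, D83.9 | D83.0 |

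Three of the ten D80 positions are listed. Which of the others are valid and relevant codes is a question for the ICD-10-CM manual.

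**4. Where such a subject goes.** A subject coded only D83.0 meets no diagnosis group (1-8) and not group 9. Groups 10 and 11 need more than 14 days of qualifying drug use. Without it, the subject is non-IC. With it, or with any other listed IC diagnosis, the subject is IC but not in this group on the strength of D83.0.

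**5. Effect on the non-IC rate.** Let f be the share of non-IC person-time that comes from missed cases and RR their breakthrough rate ratio. The observed rate is the true rate times (1 - f) + f × RR = 1 + f × (RR - 1), so the inflation is f × (RR - 1). The documents give neither quantity; the values below are assumed.

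- f = 0.01%, RR = 2: 0.0001 × 1 = 0.01%
- f = 0.1%, RR = 2: 0.001 × 1 = 0.1%
- f = 0.1%, RR = 10: 0.001 × 9 = 0.9%
- f = 0.5%, RR = 10: 0.005 × 9 = 4.5%

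The effect on the group's own rate and VE cannot be computed, because no counts by code are given.

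**The case against.** The strongest reply is that the eculizumab line is a layout matter. It has no code, it follows the D84.1 row, cell structure may have been lost in reading the PDF, and the figure showing the algorithm is not available. The Table 1 claim minimum also argues against a separate drug route. This stands as a reason not to assert that eculizumab users without a diagnosis are admitted. It does not remove the conflict, because a qualifier on D84.1 also breaks the diagnosis-only rule. The line might instead be meant as a descriptive treatment stratum. However, the dialysis rows of the same annex tie such strata explicitly to the codes above them, and this line does not.

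A second reply is that the plan partly covers the matter. Section 8.9 concedes that the accuracy of the modified algorithm is unknown, section 8.7 foresees varying the IC case definition, section 8.5 calls the study mainly descriptive, and VE is exploratory. This limits the consequences. But a general caveat does not replace correcting a list that can be corrected, and no sensitivity analysis of these codes is named.

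A reader might infer more, namely that likely poor responders to vaccine are being counted as non-IC because of how this group is built. The documents do not support that. The eculizumab line, as a separate route, can only add people to IC. The documents also do not say what the missing D80 codes or D83.0 denote, whether D80.8 is the right entry for its label, what else D84.1 covers, or how such patients respond to vaccination. Nor do they show that the group is filled with milder or acquired states. An attempt to size dilution of the group's rate ratio would model people wrongly included, not codes left out, and would need inputs the documents lack.

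**Conclusion.** The concern holds in a limited form. Annex 3 conflicts with sections 8.2.1 and 8.3 on whether drug use enters the primary immunodeficiency group, under either of the two main readings. D83.0 and seven of the ten D80 positions fall in no IC group, so subjects coded only with them and without qualifying drug use go to the non-IC comparator. This is more than missing detail, because following the list as written puts those subjects in the wrong cohort relative to the row's own label, most plainly for D83.0.

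The damage is mainly to the completeness and composition of one planned subgroup, and its size there is unknown. For the pooled non-IC rate it is probably small: at most 0.9% for f up to 0.1% and RR up to 10, and 4.5% at the extreme assumed corner of f = 0.5% and RR = 10. It would be too strong to say that the group can contribute nothing to the question in section 6. Incomplete capture narrows what the group represents but does not by itself invalidate its rate.

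**What to change.** 1. Make the group diagnosis-only by taking the eculizumab line out and handling it under the immunosuppressive-medication rules. Alternatively, amend sections 8.2.1 and 8.3 to state the drug route, and say how it interacts with group 10.
2. Add D83.0, so that the common variable immunodeficiency row covers all of D83.
3. Check the D80, D81 and D84 entries against the ICD-10-CM manual before the run, and correct or justify each omission.
4. Name, among the IC-case-definition sensitivity analyses already foreseen in section 8.7, one that reports this group with the full D80-D84 range.

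The cost is a code-list edit and a rerun, which the monthly data cuts make easy to accommodate. The downside is that the group size changes and comparability with any earlier data cut is reduced, so the report should say from which cut the revised list applies.
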